If new elevations in ALT or AST >3 times ULN, **without** an elevation of total serum bilirubin >2 times ULN are identified, the following steps are to be taken:

- Temporary discontinuation of Investigational Medicinal Product (IMP);
- Repeat testing of ALT, AST, ALP, and total bilirubin, should be completed within 48 to 72 hours to confirm the abnormalities and to determine trend;
- IMP should not be resumed until monitoring indicates abnormalities have resolved or have stabilized.

Details on the management of subjects with other ALT and AST abnormalities are further described in [Section 9.4, Study Medication Stopping Rules](#).

Worsening of Anemia – In this study, it is possible that some subjects may experience a worsening of anemia. As the primary endpoint of this study assesses Hb response, worsening of anemia is captured as part of this efficacy parameter. Worsening of anemia should not be

considered an AE unless the worsening of anemia is associated with a cause *other than* the subject's CKD.

Transplantation – During this long-term study, it is anticipated that some subjects may receive a kidney transplant. These events will not be recorded as AEs. Subjects will discontinue study medication for receipt of a kidney, other solid organ, hematopoietic stem cell or bone marrow transplant and should continue with the Schedule of Activities and safety assessments as described in [Section 7.5.5.2, Permanent Discontinuation of Study Medication](#).

Malignancy – During this long-term study, some subjects may develop a newly diagnosed malignancy or a recurrence of a malignancy. At the discretion of the Investigator, these subjects may continue study medication (vadadustat or darbepoetin alfa). For reporting of adverse events of malignancy, see [Section 10.1.2 Serious Adverse Events](#).

Renal-Related Events - Some subjects will experience a progression of their CKD over the course of this study as part of the natural course of the disease. In addition, the study population is prone to experience acute, transient loss of kidney function of different etiologies, sometimes concomitantly complicated by progression of CKD.

To ensure consistent reporting of renal events, the following guidelines are to be used when reporting a renal-related AE:

- The following situations **should always be reported as SAEs** with seriousness criterion “medically important,” if no other seriousness criteria are met (see Section 10.1.2, Serious Adverse Events):

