10.1.2 Serious Adverse Events

Each AE is to be classified by the Investigator as SERIOUS or NONSERIOUS. An AE that meets 1 or more of the following criteria/outcomes is classified as serious:

- Death
- Life-threatening (see paragraph below on life-threatening)
- In-patient hospitalization or prolongation of existing hospitalization (see paragraph below on hospitalization)
- Persistent or significant disability/incapacity (see paragraph below on disability)
- Congenital anomaly/birth defect
- Is considered a medically important event not meeting the above criteria, but which may jeopardize a subject, or may require medical or surgical intervention to prevent one of the criteria listed in this definition.

In addition to the above criteria for classifying AEs as serious, the following situations will also be classified as serious for purposes of this study:

- Dialysis or Transplantation – Events requiring transition to chronic, ongoing dialysis, or requiring an acute transient course of dialysis, or requiring an immediate kidney transplantation (ie, not pre-planned) will be classified as serious. Guidance for the reporting of these events is provided in [Section 10.1.1, Adverse Events](#).
- Malignancies – Newly diagnosed malignancies or a recurrence of a malignancy should be reported as an SAE with the seriousness criterion “medically important” if no other seriousness criteria are met. If a subject develops basal cell carcinoma of skin, squamous cell carcinoma of skin, or cervical carcinoma in situ during the study, or has worsening of these events from Baseline, the Investigator will determine if the event is reported as an AE or SAE.
- Designated Medical Events - The sponsor maintains a list of designated medical events (DME) that they will always classify as serious adverse events. If an event on the DME list is reported as an AE additional information on the event (e.g. investigator confirmation of seriousness, causality) will be requested from the Investigator.

Serious also includes any other event that the Investigator or Sponsor judges to be serious. If there is any doubt whether the information constitutes an AE or SAE, the information is to be treated as an SAE.

The Sponsor has a list of events that they classify as “always serious” events. If an AE is reported that is considered to be an event per this classification as “always serious”, additional information on the event may be requested.

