10.3.5 Relationship to Study Medication

The causal relationship of the AE to study medication (vadadustat or darbepoetin alfa) will be assessed by both the Investigator and the Sponsor.

The assessment of causal relationship to study medication should be evidence-based, and not based on the premise that all AEs are possibly causally related to study medication until proven otherwise.

Examples of evidence that would suggest a causal relationship between the study medication and the AE include the occurrence of an AE that is uncommon and known to be strongly associated with drug exposure (eg, angioedema, hepatic injury, and Stevens-Johnson syndrome) or an AE that is uncommon in the population exposed to the drug.

The causal relationship of the AE is assessed using a binary system, and AEs are classified as either ‘related’ or ‘unrelated’:

Related: There is ‘reasonable possibility’ that the drug caused the AE. The AE follows a reasonable temporal sequence from the time of drug administration. There is supportive evidence (facts) to suggest a possible causal relationship, irrespective of the degree of certainty between the observed AE and the drug.

Unrelated: An AE does not follow a reasonable temporal sequence from administration of the product and/or there is no reasonable possibility that the drug caused the AE. This assessment includes situations where the AE is related to other factors such as the subject’s clinical state, other therapeutic interventions, or concomitant drugs administered to the subject.

Default assessments using the “related” category without supportive evidence for a causal relationship to study medication is generally uninformative and does not contribute meaningfully to the development of the safety profile of the drug or to subject protection.

Investigators are encouraged to choose the most plausible cause for the event(s) from the following list: medical history, lack of efficacy/worsening of treated condition, study medication, other treatment (concomitant or previous), withdrawal of study medication, administration error, protocol-related procedure, and others (specify).

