11 DATA ANALYSIS

Data collected throughout the study will be summarized using descriptive statistics and listed in by-subject listings. Continuous variables will be summarized using number of subjects with data, mean, standard deviation, median, minimum, and maximum. For categorical variables, the number and percentage of subjects in each category will be tabulated. Summaries will be provided by treatment group within appropriate analysis populations (as defined in [Section 11.2, Study Analysis Populations](#)) and by time point/time period as appropriate.

For Hb, Baseline will be calculated as the average of the central laboratory Hb measurements of samples taken at the screening visit closest to the date of randomization and the measurement taken at randomization.

For other parameters, unless otherwise specified, Baseline will be defined as the last available value prior to the first dose of study medication.

Hemoglobin values as assessed through the central laboratory will be used for efficacy and safety evaluations; local HemoCue Hb values will be used only for dose adjustments.

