11.6.1 Analysis of Primary Efficacy Endpoint

The primary efficacy endpoint is defined as the mean Hb change from Baseline (mean pretreatment Hb) to the mean Hb from Weeks 24 to 36 (inclusive).

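### Worsening CKD anemia is excluded from AEs with no exception for serious cases, while neighbouring rules point toward reporting it, and the reason given for the exclusion does not cover most of the reporting period

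*Protocol*

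**What the plan says.** Section references are to Amendment 7 of the protocol.

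- **The exclusion.** Section 10.1.1 (Worsening of Anemia) says such worsening should not be "considered an AE unless the worsening of anemia is associated with a cause" other than CKD. The reason given is that "worsening of anemia is captured as part of this efficacy parameter", meaning the primary endpoint. Serious cases are not mentioned.
- **The SAE definition.** Section 10.1.2 opens with "An AE that meets 1 or more of the following criteria/outcomes is classified as serious" and lists "In-patient hospitalization or prolongation of existing hospitalization" among the criteria. It later adds that anything the investigator or sponsor considers serious also counts, and that doubtful cases are handled as SAEs.
- **The general AE rules.** Elsewhere in 10.1.1, worsening of an existing illness is an AE, and so is a laboratory abnormality that needs treatment.
- **The endpoint relied on.** Section 11.6.1 defines it as the change from Baseline to the mean hemoglobin over Weeks 24-36. Section 11 adds: "Hemoglobin values as assessed through the central laboratory will be used for efficacy and safety evaluations".
- **The reporting period.** Section 10.3.1 runs AE reporting from randomization to global study completion. Section 9 schedules visits to Week 208.

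**The concern.** Admission for uncontrolled anemia is a direct clinical consequence of a failing anemia treatment. On the wording of the anemia paragraph alone, an admission with that diagnosis is not an AE, so the hospitalization criterion, which applies to AEs, has nothing to act on. The Medical Diagnoses rule in 10.1.1 adds to this: fatigue or dyspnea is to be reported under its diagnosis, and here the diagnosis is the excluded one.

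A site that reads the general rules, or the closing sentences of the SAE definition, could reasonably report the same admission as an SAE. Investigators know the treatment, so the choice between the two readings could differ by site or by arm.

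Three outputs depend on it: the AE and SAE tables; the Hospitalization endpoint in Section 5.4, if it is built from SAE reports; and the IDMC's view, since Section 6.4.2 names AEs, vital signs and laboratory results as its key safety data.

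**Working it through.** The protocol states no figure for this point, so there is none to reproduce. The check has two parts.

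**1. How the rules apply to one case:** a subject admitted with symptomatic anemia that the investigator attributes to CKD.

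| Rule | Direction |
|---|---|
| 10.1.1, Worsening of Anemia | Not an AE |
| 10.1.1, Medical Diagnoses | Symptoms reported under the diagnosis, which is excluded |
| 10.1.1, worsening of an existing illness or condition | AE |
| 10.1.1, laboratory value needing treatment | AE |
| 10.1.1, CKD complication without decline in kidney function | Report the complication |
| 10.1.2, hospitalization criterion | Serious, if it is an AE |
| 10.1.2, judged serious, or in doubt | SAE |

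Nothing says which rule prevails. For progression of CKD not requiring dialysis, which is also expected disease, 10.1.1 does settle the matter: it is an SAE when a seriousness criterion is met.

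**2. How much of the reporting period the cited endpoint covers.**

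Inputs: the primary window is Weeks 24-36, or 12 weeks (13 if both end weeks are counted). The key secondary window is Weeks 40-52, of the same length. Scheduled post-baseline visits are 16 in Year 1 and 4 in each of Years 2, 3 and 4, so 16 + 12 = 28. The primary window holds Weeks 24, 28, 32 and 36; the secondary holds Weeks 40, 44, 48 and 52.

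Formula: coverage = window length / follow-up. Follow-up is event-driven, so a range is shown.

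| Follow-up | Primary window | Both windows |
|---|---|---|
| 52 weeks | 12/52 to 13/52 = 23-25% | 24/52 to 26/52 = 46-50% |
| 104 weeks | 12/104 to 13/104 = 12-13% | 24/104 to 26/104 = 23-25% |
| 156 weeks | 12/156 to 13/156 = 8% | 24/156 to 26/156 = 15-17% |
| 208 weeks | 12/208 to 13/208 = 6% | 24/208 to 26/208 = 12% |
| By visits | 4/28 = 14% | 8/28 = 29% |

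Weeks 0-23, when subjects entering with a mean screening hemoglobin below 10.0 g/dL are being titrated, lie outside both windows. So does everything after Week 52. Inside the window, Section 11.5 keeps hemoglobin measured after rescue in the average, so a treated episode can be masked. A nadir measured by a hospital's own laboratory does not enter the endpoint, which uses central-laboratory values.

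**The case against.** The strongest reply is that the trial does track worsening anemia, though not as an AE. Hemoglobin below 8.0 g/dL is a safety endpoint with no window (5.4). A central blood count is drawn at every scheduled visit. Transfusions and ESA rescue are collected at each visit with reasons on the case report form, and worsening anemia due to CKD is a named transfusion reason (8.4.7). Lack of efficacy is a recorded reason for discontinuation (7.5.5). Admissions with their own diagnosis, such as heart failure or myocardial infarction, remain reportable, and deaths are MACE. Anemia from another cause is still an AE. All of this stands, and it confines the loss to the AE and SAE data. But none of these records is described as showing that an admission took place, and the visit procedures in 9.3.5 to 9.3.10 list no separate collection of hospitalizations.

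A reader might go further in several ways that the protocol does not support:

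- *Every such admission is lost.* The closing sentences of 10.1.2 and the general rules in 10.1.1 give sites a route to report. The defect is contradiction, not certain loss.
- *Worsening goes uncaptured for about 88% of the trial.* That figure is 1 - 24/208. It uses the longest schedule and ignores the other records above.
- *Section 10.3.5 contradicts the exclusion by listing "lack of efficacy/worsening of treated condition" as a cause.* It does not. A separate event can be caused by worsening anemia without the worsening itself being an AE.
- *A definite number of SAEs is missing.* Assuming 1-3% of subjects are admitted would give 9-28 per arm of 925 (0.01 x 925 to 0.03 x 925), but the protocol has no source for that rate, and the count supposes that no site reports any case.
- *The SAE comparison is biased toward no difference.* That needs unequal admission rates between arms, which nothing here shows.

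More SAE reporting in an open-label trial also carries judgement, since attribution to CKD stays with the investigator. That is true, but an explicit rule leaves less to judgement than conflicting ones.

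**Conclusion.** The point holds as an inconsistency in the reporting rules combined with an inaccurate rationale. Serious worsening of CKD anemia can be omitted from the AE and SAE data, or entered unevenly. Whether the Hospitalization endpoint is affected depends on its data source, which the protocol does not state. The IDMC would still see hemoglobin among the laboratory data, but not an admission that went unreported.

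The rationale fails under every follow-up length shown: the primary endpoint covers at most 25% of the reporting period, and that maximum applies only if follow-up ends at Week 52. The number of admissions affected cannot be derived from the protocol. The primary efficacy analysis is not touched. It is worth correcting because the ambiguity bears on a core safety comparison and the remedy is small.

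**What to change.** In Section 10.1.1:

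1. Add a sentence to the anemia paragraph, for example: *Worsening of anemia due to CKD that meets any seriousness criterion in Section 10.1.2 is reported as an SAE; non-serious worsening due to CKD is not reported as an AE.* The first half follows the rule already used for serious CKD progression.
2. State that this paragraph takes precedence over the general rules on worsening conditions, laboratory values needing treatment and CKD complications, and align the closing sentences of 10.1.2 with it.
3. Replace the rationale. Non-serious worsening is followed through central-laboratory hemoglobin, the endpoint of hemoglobin below 8.0 g/dL, and the transfusion and ESA-rescue records, not through the primary endpoint alone.

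The cost is a short text change, a note to sites and a modest number of additional SAE reports. Reporting changes; treatment does not.

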Procedures – Diagnostic and therapeutic non-invasive and invasive procedures, such as surgery, should not be reported as AEs. However, the medical condition for which the procedure was performed should be reported if it meets the definition of an AE. For example, an acute appendicitis that begins during the AE reporting period should be reported as the AE and the resulting appendectomy noted under ‘Comments’.

Pre-planned therapeutic procedures not associated with a new medical condition or worsening pre-existing condition should not be reported as AEs (with the exception of kidney transplant, see below).

Pre-existing Conditions – In this study, a pre-existing condition (ie, a disorder present before the AE reporting period started and noted on the pretreatment medical history/physical examination form) should not be reported as an AE unless the condition worsens or episodes increase in frequency during the AE reporting period.

Abnormal Test Findings – All laboratory test results will be reviewed by the Investigator. The Investigator will utilize his/her judgment in determining if out of range laboratory values are clinically significant and will denote this using the abbreviation “CS” on the laboratory report for source documentation. Laboratory tests that are labeled as clinically significant should be reported as AEs, either separately or as part of a description of a symptomatic AE. If there are significant changes in a laboratory report from a previous visit that are determined to be clinically significant, these should also be reported as AEs. Any abnormal laboratory value which requires treatment or further diagnostic testing and/or results in discontinuation from study should be reported as an AE. An expected laboratory abnormality from a condition that is part of the medical history is not considered clinically significant for the purposes of the study unless it represents a worsening of the condition.

Abnormalities in ALT, AST and Total Bilirubin - Abnormalities in ALT, AST and Total Bilirubin should be reported to the Sponsor’s Medical Monitor or CRO designee within 24 hours of awareness as SAE with “medical significance” criteria selected, if the following conditions are met:

- New elevation in ALT or AST > 3 times ULN, with or without an elevation of total serum bilirubin >2 times ULN; AND

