 - **Progression of CKD leading to chronic dialysis**: When a subject undergoes transition to chronic maintenance dialysis, an SAE should be reported using the verbatim term of “end-stage renal disease” with the outcome denoted as recovered with sequelae of chronic dialysis.
 - **Any medical event requiring transient acute dialysis**: When a subject undergoes transient acute dialysis, an SAE should be reported using the verbatim term reflecting the indication for the dialysis. Examples of verbatim AE terms include: hyperkalemia, volume overload, acute kidney injury, and uremia.
 - **Kidney transplantation**: When a subject receives a kidney transplant, an SAE should be reported using the verbatim term “Progression of CKD,” with the outcome denoted as recovered with sequelae of “kidney transplant.”
- The following situations will be **reported as SAEs if they meet seriousness criteria** (see Section 10.1.2, Serious Adverse Events); otherwise, they should be reported as AEs:
 - **Acute kidney injury not requiring dialysis** – The reported AE term should reflect the etiology for the impairment of the renal function. Non-specific AE terms such as “Decreased eGFR” or “Increased creatinine” should be avoided whenever the underlying etiology is known.
 - Examples of verbatim AE terms for prerenal impairment include: hypovolemia, hepatorenal syndrome, and heart failure
 - Examples of verbatim AE terms for intrarenal impairment include: acute tubular necrosis, acute interstitial nephritis, and glomerulonephritis

- Examples of verbatim AE terms for postrenal impairment include: hydronephrosis, pelvicaliectasis, and urinary tract obstruction
- Progression of CKD not requiring dialysis – If permanent loss of renal function due to underlying CKD has occurred, the reported AE term should reflect the underlying etiology. Non-specific terms such as “Decreased eGFR,” “Increased creatinine,” or “Worsening CKD” should be avoided whenever the underlying etiology is known. Examples of verbatim AE terms include: worsening lupus nephritis, worsening diabetic kidney disease, and worsening glomerulonephritis.

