11.7.2 Analysis of Adverse Events

Adverse events will be summarized using the number and percentage of subjects with AEs for all subjects in the safety population. Summaries will also be provided for subgroups including Region, Age, Gender and Race.

All AEs will be coded using MedDRA. Treatment-emergent and post-treatment AEs will be summarized by System Organ Class and Preferred Term for each treatment group. Adverse events will also be summarized by their maximum severity.

Summaries will also be provided for the following types of AEs:

- SAEs
- Related AEs (including all categories for relationship to study medication other than “Unrelated”, as determined by the Investigator)
- AEs leading to early discontinuation of study medication

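### Section 10.1.1 gives opposite instructions on kidney transplant: not recorded as an AE, yet always reported as an SAE

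*Protocol*

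**What the plan says.** All references are to the current protocol (Amendment 7), not to the original version bound in the same file.

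- **Section 10.1.1, Procedures.** Pre-planned therapeutic procedures without a new or worsening condition are not reported as AEs, "with the exception of kidney transplant, see below".
- **Section 10.1.1, Transplantation.** The paragraph says "it is anticipated that some subjects may receive a kidney transplant" and continues: "These events will not be recorded as AEs". Study medication is discontinued and follow-up goes on.
- **Section 10.1.1, Renal-Related Events.** The guidelines open with their purpose: "To ensure consistent reporting of renal events". The first group of situations "should always be reported as SAEs". Kidney transplantation is in that group: "When a subject receives a kidney transplant, an SAE should be reported using the verbatim term" *Progression of CKD*, with the transplant recorded as a sequela in the outcome field.
- **Section 10.1.2.** Among additional situations treated as serious are events "requiring an immediate kidney transplantation (ie, not pre-planned) will be classified as serious". The item refers to Section 10.1.1 for reporting guidance.
- **Section 10.3.3.** Every SAE goes to the sponsor's medical monitor or its CRO designee within 24 hours of awareness.
- **Section 11.7.2.** "Adverse events will be summarized using the number and percentage of subjects with AEs", with further summaries for SAEs and for AEs leading to early discontinuation of study medication.

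**The concern.** Two paragraphs of one section attach opposite instructions to the same event, receipt of a kidney transplant. A site that follows the Transplantation paragraph files nothing. A site that follows the renal list files an SAE within 24 hours. Each can point to protocol text, so a monitor has no standard for calling either one a deviation.

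The case is expected to arise. The protocol anticipates transplants, Section 7.3 (criterion 12) admits subjects on a kidney transplant wait-list, and Section 7.5.5 lists transplant as a reason for stopping study medication. With approximately 390 sites (Section 6.1), different readings are a realistic possibility. What is at stake is the completeness and comparability of a serious renal event in the SAE tables, the tables by coded term, and the table of AEs leading to discontinuation, since transplant requires study medication to stop.

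**Working it through.** No arithmetic applies: the protocol states no figure for transplants and none for AE or SAE counts on this point. The check is a comparison of the text.

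**Step 1. Same event?** In the Transplantation paragraph, the events in question are the kidney transplants anticipated in the sentence just before. In the renal list, the trigger is a subject receiving a kidney transplant. The trigger is the same, and neither paragraph limits it to planned or unplanned cases.

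**Step 2. Instructions side by side.**

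| Place | Planned kidney transplant | Unplanned kidney transplant |
|---|---|---|
| 10.1.1 Transplantation | not recorded as an AE | not recorded as an AE |
| 10.1.1 Renal-Related Events | always an SAE | always an SAE |
| 10.1.1 Procedures | exempt from the rule that planned procedures are not AEs | not covered by the exemption |
| 10.1.2 | not named | serious |

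The first two rows are incompatible in both columns. An SAE is an AE, so an event cannot be left unrecorded as an AE and also be reported as an SAE.

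**Step 3. Does the Procedures paragraph settle it?** Its exemption implies that even a planned kidney transplant is reportable, and it sends the reader further down the section. The first transplant text found there is the Transplantation paragraph, which says the reverse.

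**Step 4. Does Section 10.1.2 settle it?** Its list adds to the general seriousness criteria, so it is narrower than the renal list without contradicting it. For reporting it refers back to Section 10.1.1, where the conflict lies.

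**Step 5. How far does the effect reach?**

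- Affected: transplant-triggered SAEs, their 24-hour reporting (10.3.3), and the AE and SAE summaries in 11.7.2.
- Not affected: the rules for chronic dialysis and transient acute dialysis, which agree between 10.1.1 and 10.1.2; the hemoglobin analysis (11.6.1.1); MACE (11.7.1); and the sample size (11.1).

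**The case against.** The best defence separates procedure from condition. The Procedures paragraph says that procedures are not AEs but that the condition behind them is. The renal list has that shape: the reported term is CKD progression and the transplant appears only as the outcome. The Transplantation paragraph would then mean only that the operation itself is not an AE. This is a plausible intention, but the text does not state it. The renal SAE is triggered by receipt of the transplant, and the Procedures paragraph removes kidney transplant from the rule on which this reading depends.

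It can also be said that the renal list is the more specific rule, and that Section 10.1.2 tells sites to treat an event as an SAE when they doubt whether it is an AE or SAE. That helps a site that has noticed the conflict. A site that has read only an express instruction not to record the event has no doubt to resolve.

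Three objections limit the consequences, and they stand:

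- Transplants are not invisible. Transplant is a listed reason for stopping study medication, and Section 11.4 tabulates those reasons. That route does not replace the AE record, and it would not show a transplant in a subject who had already stopped study medication.
- Section 11.7.2 counts subjects. Someone who has already gone to chronic dialysis should already have an SAE of end-stage renal disease, so a missing transplant report would not change that subject's overall SAE status.
- Criterion 12 excludes subjects with a transplant already scheduled at entry, which narrows the planned category.

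A reader might infer more than the documents support:

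- **Section 10.1.2 as a third conflicting rule.** It is additive and does not say that only unplanned transplants are serious.
- **Contamination of the secondary endpoint on CKD progression.** Section 5.3 lists that endpoint, but nothing in the current text derives it from AE terms.
- **A between-arm bias.** The trial is open-label, so differential reporting is possible. But the same text governs both arms, a site's reading would ordinarily apply to all its subjects, and no differential mechanism is shown.

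**Conclusion.** The contradiction is real and is in the current text. Sites may report or omit transplant-triggered SAEs depending on the paragraph they follow. That they will differ is an inference from the wording and the number of sites; the protocol does not say so.

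The number of affected events cannot be estimated. Someone might assume that 1% to 3% of the 1850 planned subjects are transplanted, giving 0.01 × 1850 = 18.5 to 0.03 × 1850 = 55.5, or about 19 to 56 subjects. The protocol contains no transplant rate to support that range, and not every omitted report would change a subject-level count. Such a figure would be at best an upper bound under an assumed rate, and the finding does not rest on it.

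The correction should still be made. It goes beyond a missing detail, because following one stated rule breaches another that carries a 24-hour duty. The analysis plan could not repair it, because events never reported as AEs cannot be recovered from the AE data. The conclusions on hemoglobin and MACE do not depend on it.

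**What to change.** Reconcile four places to one reporting rule that covers both planned and unplanned kidney transplants: the Procedures, Transplantation and Renal-Related Events paragraphs of Section 10.1.1, and the dialysis or transplantation item of Section 10.1.2. One way is to remove or amend the sentence "These events will not be recorded as AEs" so that it agrees with the renal list, and to align 10.1.2 with it. The sponsor may choose a different single rule, provided all four places state it. If the intended distinction is between the operation and the underlying disease, the text should say so.

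Notify sites of the chosen rule, and state how it applies to transplants that have already occurred. A planned/unplanned flag on the CRF would let the tables separate the two kinds, but it is optional and is not needed to remove the conflict.

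The cost is a protocol wording correction and a site memo, plus one CRF field if the flag is wanted.
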